## I. Project Title

Difference in aerosol-generating amount between wired magnetic-assisted capsule endoscopy system and esophagogastroduodenoscopy examination of varices in biliary atresia patients

## IV. Specific Aims

The goal of this clinical trial is to compare the safeness and effectiveness of traditional esophagogastroduodenoscope (EGD) and wired magnetically assisted capsule endoscopy (MACE) in the diagnosis of esophageal varices in biliary atresia (BA) patients.

## V. English Abstract

**Background and aims:** Biliary atresia (BA) is the leading cause of chronic liver insufficiency, liver cirrhosis, esophageal varices, and liver transplantation in the world. Regular endoscope examination with prompt adjustment of therapeutic agents is key to avoid the occurrence of esophageal varices bleeding. During the pandemic of COVID-19, to offer a regular and safe endoscopy survey of esophageal varices in BA patients become a medical challenge issue in the world.

Our study aim to investigate the diagnostic utility and safety of a Magnetically Assisted Capsule Endoscopy (MACE) system as comparing with traditional esophagogastroduodenoscope (EGD) in BA patients for the esophageal varices survey. We also aim to clarify whether the MACE is a less aerosol -generating procedure than EGD during the survey of esophageal varices, and decrease the risk of SARS-CoV 2 transmission.

**Methods:** This is an open-labeled un-blind trial. We intend to include 25 BA patients > 6 years of age agree to receive MACE examination into the study group, and another 25 BA patients > 6 years of age

Approval Number: 202210059DIPA

who will receive regular EGD into the control group. After the signature of the informed consent, they will enter this study. During the examination, a DR-528 Handheld Particle Counter (Met One Instruments, Inc., Grants Pass, OR) will be applied to detect aerosol generated during the examination. The compliance, diagnostic accuracy, and safety between study and control groups will be analyzed.

**Scientific merits and anticipated results:** The MACE was approved to achieve similar diagnostic accuracy and safety as EGD in adult population in Taiwan. Since subjects receiving MACE examination may close their mouth and have a face mask during the procedure, we intend to prove the MACE is an efficient, safe and less aerosol-generating procedure than EGD in BA patients this study. With the results of this study, we may offer the evidence of a safe and efficient examination during the pandemic of COVID-19 to protect the patients and medical staffs.

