## VI. Background Introduction & Significance

**Research Purpose:** Our study aims to investigate the diagnostic utility and safety of the Magnetically Assisted Capsule Endoscopy (MACE) system compared to traditional esophagogastroduodenoscopy (EGD) in the surveillance of esophageal varices in patients with biliary atresia (BA). Additionally, we seek to determine whether MACE generates fewer aerosols than EGD during the examination, thereby potentially reducing the risk of SARS-CoV-2 transmission.

**General Background Information:** Biliary atresia (BA) is one of the leading causes of chronic liver failure, liver cirrhosis, esophageal varices, and the need for liver transplantation during childhood worldwide (1-4). Statistically, approximately 50% of patients with BA develop portal hypertension, and 26.5% are at risk of gastrointestinal variceal bleeding (5-7). Esophageal variceal bleeding often results in significant complications and risks. In adult patients with chronic hepatitis, clinical indicators such as APRI, FIB-4, Extended Baveno, or Baveno VI are commonly used to help predict the presence of significant esophageal varices (8, 9). However, previous studies in BA patients have shown that these clinical indicators are not accurate in predicting the risk of esophageal varices in this population. Therefore, in clinical practice, physicians still rely on invasive esophagogastroduodenoscopy (EGD) to diagnose and assess the severity of esophageal varices. Based on the severity of the esophageal varices, physicians adjust medication dosages to reduce the risk of unexpected variceal bleeding and its associated complications.

Since the outbreak of SARS-CoV-2 in Wuhan, China in 2019, COVID-19 has continued to spread widely across the globe and has been confirmed as a direct contact and droplet infection disease. As of

Approval Number: 202210059DIPA

June 2022, COVID-19 has resulted in nearly 541 million infections and over 6.3 million deaths worldwide. In Taiwan, it has caused 3.44 million infections and more than 6,000 deaths. Consequently, the pandemic has placed enormous pressure and strain on global healthcare systems. During the outbreak in Europe in 2021, it was reported that over 20% of healthcare workers in northern Italy were infected, severely disrupting normal medical operations and preventing patients with chronic illnesses from receiving necessary medical care (10).

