## VIII.Experiment Designs & Methods

### (I.) Patient eligibility

#### A.Inclusion criteria:

- (A.) Biliary atresia patients > 6 years old
- (B.) Vital signs are stable
- (C.) Without acute gastrointestinal bleeding

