#### B.Exclusion Criteria:

- (A.) Patients with metal implants, metal stent, artificial joints, bone plates, and bone screw
- (B.) Patients with electronic devices, such as pacemakers, cochlear implants, or other

Approval Number: 202210059DIPA

implanted electronic medical devices

- (C.) Throat or esophageal obstruction leading to dysphagia patients
- (D.) Consciousness disturbance patients unable to swallow
- (E.) Patients with acute upper gastrointestinal bleeding
- (F.) Patients with platelet lower than 40K or PT INR > 1.5

(II.) Design of experiments:

A. Study Design: Prospective open-label trial.

B. Trial Procedure:

(A.) Endoscopic Examination

In this study, 25 patients aged 6 years or older with biliary atresia undergoing Magnetic-Assisted Capsule Endoscopy (MACE) for esophageal varices survey will be enrolled as the "study group," while another 25 patients aged 6 years or older with biliary atresia undergoing conventional esophagogastroduodenoscopy (EGD) for esophageal varices survey will be enrolled as the "control group." Both groups will prospectively enter the study after providing informed consent and signing the consent form. All patients will fast appropriately according to endoscopic examination guidelines before the procedure. Patients undergoing conventional EGD may choose to receive conscious sedation based on clinical needs. Patients undergoing MACE will be advised to keep their lips closed and wear a surgical mask during the examination. We will compare clinical parameters between the two groups, including examination completion rate, pain perception during the procedure, safety, and willingness to undergo the same examination again in the future.

(B.) Droplet Particle Measurement

During examinations in both the "study group" and the "control group," we will use the MET ONE airborne particle counter [DR-528 Handheld Particle Counter (Met One Instruments, Inc., Grants Pass, OR)], placed on a platform at the same horizontal level as the patient lying flat, to simultaneously measure the number of droplet particles generated during the procedure. We will then compare the differences in droplet particle counts between the two groups. The primary endpoint of this study is to analyze the

Approval Number: 202210059DIPA

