difference in the number of droplet particles generated during the examinations between the "study group" and the "control group." The secondary endpoints are to analyze the examination completion rate, pain perception during the procedure, safety, and willingness to undergo the same examination again between the two groups.

(C.) Project Period: 11/01/2022-12/31/2026 (MM/DD/YYYY)

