**XI. Methods for Data Collection, Processing, Evaluation, and Statistical Analysis**

**Approval Number: 202210059DIPA**

(I.) Collect and record the enrolled patients' basic information (including sex, age, height, weight, past medical history, and medication history), vital signs, pain index, blood test results within the past three months, and transient elastography values.

(II.) Document the examination results of both the Magnetically Assisted Capsule Endoscopy (MACE) and conventional esophagogastroduodenoscopy (EGD), including the presence of esophageal varices and bleeding sites.

(III.) Record the patients' acceptance of the examination and any adverse effects.

(IV.) Record the particle count measurements obtained using the MET ONE Airborne Particle Counter [DR-528 Handheld Particle Counter (Met One Instruments, Inc., Grants Pass, OR)].

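### The MACE and EGD groups are not formed by randomisation or matching, yet only unadjusted two-sample tests are planned, so the comparisons may be confounded

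*Combined protocol and SAP*

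**What the plan says.** Section V defines the study group as "25 BA patients > 6 years of age agree to receive MACE examination into the study group" and the control group as patients who are to have regular EGD. Section VIII(II)B(A) again defines the groups by the examination undergone; the controls are "another 25 patients aged 6 years or older with biliary atresia undergoing conventional esophagogastroduodenoscopy (EGD) for esophageal varices survey". Section VIII(II)A calls the design prospective and open-label. The sections on design, procedures, data collection and statistics mention no randomisation, matching or stratification.

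The inclusion criterion is "Biliary atresia patients > 6 years old", with no upper limit, so children and adults may be mixed.

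Section VI introduces aerosol as an additional question ("we seek to determine whether MACE generates fewer aerosols than EGD during the examination"), but section VIII(II)B(B) makes the between-group difference in particle count the primary endpoint. It then adds: "The secondary endpoints are to analyze the examination completion rate, pain perception during the procedure, safety, and willingness" to repeat the examination.

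Section XI(I) collects "basic information (including sex, age, height, weight, past medical history, and medication history", together with recent blood tests and elastography. No analytic use of these is stated. Section XII names the t-test or Mann-Whitney test for continuous variables and chi-square or Fisher's exact test for categorical ones, at p<0.05.

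**The concern.** Patients who agree to swallow a tethered capsule may differ from those who have regular EGD in ways that also affect the outcomes. Age and body size are plausible examples: they can vary widely here, and both could bear on particle emission or on reported pain. A two-sample test attributes any such difference to the device.

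The abstract says the study intends to prove that MACE is efficient, safe and less aerosol-generating. That is a causal statement, and a crude contrast of groups formed by agreement does not support it without qualification. The secondary endpoints are more exposed than the primary one, because the plan assumes no large effect for them.

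Two related features would not be cured by adjusting for age and weight. First, "Patients undergoing conventional EGD may choose to receive conscious sedation based on clinical needs"; sedation is not mentioned for MACE, and it bears on the pain comparison. Second, agreement to MACE helps define the study group, while willingness to repeat the examination is an endpoint.

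**Working it through.** **The plan's own figure.** Section XII gives 50 patients from 87-90% filtration, 95% confidence and a 5% margin. The single-proportion formula n = z²p(1−p)/0.05² gives 174 at p = 0.87 and 139 at p = 0.90, so 50 is not reproduced. That is a separate matter, and nothing below depends on it. From the plan I use only 25 per group, the 0.05 level (taken as two-sided) and the 87-90% figure.

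**Assumed inputs.** The documents give no SD, imbalance or covariate effect. I assume a binary factor present in 60% v 40%, or 70% v 30%, of the two groups, which shifts the outcome by g = 0.5 or 1 within-level SD.

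**Step 1: false positives with no true effect.** The bias is (p₁ − p₀)g. The factor also adds variance, so the within-group SD is √(1 + g²p(1−p)). For 70/30 and g = 1, the bias is 0.4, the SD is √1.21 = 1.10, and the standardised bias is 0.4/1.10 = 0.36. Putting this into the noncentral t distribution (48 df, noncentrality = standardised bias × √12.5) gives:

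| Split | g | Standardised bias | Crude, formula | Crude, simulation | Adjusted, simulation |
|---|---|---|---|---|---|
| 60/40 | 0.5 | 0.10 | 6.3% | 6.5% | 5.0% |
| 60/40 | 1 | 0.18 | 9.5% | 9.9% | 5.0% |
| 70/30 | 0.5 | 0.19 | 10.4% | 10.2% | 5.1% |
| 70/30 | 1 | 0.36 | 24.3% | 24.1% | 4.8% |

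The simulations use 20,000 runs per row. The adjusted column sits at 5% by construction, because the simulated confounder is the one adjusted for.

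**Step 2: coverage.** In the same four cases, in table order, the crude 95% CI covers the true effect about 93-94%, 90%, 90% and 75-76% of the time.

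**Step 3: the primary endpoint on the plan's premise.** Filtration of 87-90% means a ratio of 0.13-0.10, or a log difference of 2.04-2.30. With an assumed log-SD of 1, power is near 100% even with a bias of 0.4 SD in either direction. With log-SD 2 and 87% filtration, d = 2.04/2 = 1.02 and power is 94%. Bias toward no effect of 0.2 or 0.4 SD lowers it to 81% or 57%; bias the other way raises it to 99% or nearly 100%.

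The estimate moves in every case. The ratio is multiplied or divided by exp(bias × log-SD), from exp(0.2 × 1) = 1.22 to exp(0.4 × 2) = 2.23. A true 0.13 is then estimated as 0.11 or 0.16 in the mildest case, and as 0.06 or 0.29 in the most extreme.

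These figures presume negligible room background. If background is k times the EGD emission, a raw-count ratio of 0.13 becomes (0.13 + k)/(1 + k): 0.57 at k = 1 and 0.86 at k = 5 (k is assumed).

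**Step 4: willingness.** Suppose true willingness is 60% in both groups, but selection raises the MACE group to 70, 80 or 90%. Fisher's test is then significant in 7, 23 or 59% of trials, against 3% with no selection. If selection acts on both groups the effect shrinks: 80% v 80% gives 2%, and 80% v 70% gives 7%.

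**Step 5: limit of adjustment.** A second, unmeasured factor split 70/30 leaves a false-positive rate of about 10% (0.5 SD) to 21-22% (1 SD) after adjusting for the first.

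**The case against.** The protocol never claims randomisation. It states openly how the groups form, so this is a weak analysis of a declared open-label design and not a contradiction. That is right, and the point is confined to the analysis and to the strength of the conclusions.

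Nothing in the documents links age or weight to particle count, and every imbalance and SD above is assumed. This also stands. A reader might infer that the trial is biased in favour of MACE, or that the aerosol finding would be reversed. The documents support neither: the direction is unknown, and an effect of the size assumed in section XII would probably survive.

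A reader might also infer that sedation is an allocation confounder. It is mentioned as an option within the EGD procedure, so randomising would not remove it; it needs reporting, not adjustment.

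Finally, one might prescribe a log model of raw counts with a constant added for zeros. That does not hold up. The counter stands on a platform in the room, so raw counts include ambient particles that pull the ratio toward 1, possibly by more than the confounding illustrated. How background is handled is a separate question to settle first.

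**Conclusion.** The concern holds in limited form. The groups are formed by agreement to, or receipt of, the examination, and the planned tests cannot correct an imbalance in variables that the study already collects. Following section XII exactly can therefore give a confounded estimate. The omission is certain from the text; the size of its effect is not. The 6-24% range is conditional on the assumed splits and effects, and is not a prediction for this trial.

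For the primary endpoint the main risk is a distorted ratio and interval if the effect is large, and a spurious or hidden difference if it is small or absent. Adjustment for age and weight reduces the problem only in part. The plan should be changed, but this does not invalidate the study.

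**What to change.** In section XII:

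- Add a regression of the particle-count endpoint on group, adjusted for age and weight, on a suitable scale, as the main estimate with its 95% CI. Keep the crude test as a sensitivity analysis. Settle background handling first, as a separate item.
- Fix the covariates before the particle data are analysed. If data have already been seen, label the adjusted analysis post hoc.
- Analyse pain with the same adjustment, and report EGD sedation use beside it as part of the procedure.
- Report completion, safety and willingness descriptively with 95% CIs, noting that agreement to MACE helps define the study group and so may affect willingness.
- Tabulate baseline characteristics by group, including blood tests and elastography.
- Word conclusions as associations from a non-randomised comparison with only partial adjustment.

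Random allocation would be the stronger remedy, but with "Project Period: 11/01/2022-12/31/2026" it may no longer be available for some or all patients.

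The cost is about a paragraph of text, with no new visits or measurements. Two of the 48 error degrees of freedom are used. The interval may widen: if the covariates explain 10, 20 or 30% of group membership, the factor √(1/(1−R²)) is 1.05, 1.12 or 1.20, before any gain from covariates that predict the outcome. Confounding by unmeasured factors remains, and the conclusions become more cautious.

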Therefore, how to balance the medical needs of patients with biliary atresia (BA) and ensure that they receive necessary endoscopic examinations during the pandemic, while protecting both patients and endoscopy personnel from COVID-19 infection to maintain the proper functioning of healthcare systems, has become an important medical issue. Magnetic-assisted capsule endoscopy (MACE) is a novel design that utilizes a disposable, externally magnetically controlled capsule connected by a tether to guide its movement through the gastrointestinal tract (22, 23). Previous studies conducted in Taiwan have already demonstrated the safety and diagnostic accuracy of MACE for upper gastrointestinal examinations (22, 23), while also avoiding the risks associated with anesthesia. Although MACE requires swallowing a tether, its invasiveness remains significantly lower than that of conventional endoscopy. Preliminary studies have shown favorable safety and patient acceptance (22, 23). During the examination, the patient swallows the capsule similarly to taking a pill, and can keep their lips closed and wear a mask throughout the procedure.

Approval Number: 202210059DIPA

This study aims to evaluate whether MACE can achieve diagnostic performance comparable to traditional EGD in detecting esophageal varices in BA patients, while reducing aerosol generation during the procedure, thereby protecting both patients and endoscopy personnel from the risk of SARS-CoV-2 infection.

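### Diagnostic accuracy and comparability of MACE with EGD are promised, but the two examinations are described in different patients with no reference examination, so neither can be estimated as written

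*Combined protocol and SAP*

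**What the plan says.** **What is promised.** Section IV makes it the trial's goal to "compare the safeness and effectiveness of traditional esophagogastroduodenoscope (EGD) and wired magnetically assisted capsule endoscopy (MACE) in the diagnosis of esophageal varices". Section V, under Methods, says: "The compliance, diagnostic accuracy, and safety between study and control groups will be analyzed". Section VI closes with the aim to "evaluate whether MACE can achieve diagnostic performance comparable to traditional EGD in detecting esophageal varices in BA patients". Sections V and VI also speak of diagnostic utility.

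**What is described.** Section V says: "We intend to include 25 BA patients > 6 years of age agree to receive MACE examination into the study group"; another 25 patients having EGD form the control group. Section VIII (II.)B.(A.) and section XII repeat the split of 25 and 25. The trial is described as prospective and open-label (section V: "This is an open-labeled un-blind trial"), and no randomisation is mentioned. Section VIII makes the particle count the primary endpoint. The secondary endpoints are completion, pain, safety and willingness to repeat the examination; none is diagnostic. For categorical variables, section XII names only the chi-square and Fisher's exact tests, and it gives no margin.

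**What might bear on a reference.** Section XI records blood tests, transient elastography, and the varices findings of *both* MACE and EGD. Section IX lists 50 MACE sets. Section VI says of clinical indicators that "these clinical indicators are not accurate in predicting the risk of esophageal varices in this population", and that "physicians still rely on invasive esophagogastroduodenoscopy (EGD) to diagnose and assess the severity of esophageal varices".

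**The concern.** Accuracy is measured against each patient's true varices status. The plan relies on EGD for that status, but the MACE patients are not said to have EGD. The blood tests and elastography are not named as a substitute, and section VI itself says that clinical indicators are not accurate for varices in this population.

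What remains is the proportion of patients with varices reported in each of two different groups. That proportion mixes how well the procedure detects varices with how many patients have them. Difference tests without a margin cannot turn similar proportions into evidence of comparable performance.

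At stake is the diagnostic half of the stated goal. Section VI explains that treatment is adjusted according to the severity of varices, so an unsupported claim that MACE detects them as well as EGD would matter to patients.

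**Working it through.** **Inputs.** From the documents: 25 patients per group, unpaired tests, threshold 0.05 (taken as two-sided). The documents give no varices prevalence; section VI gives only about 50% with portal hypertension. Prevalence is therefore an assumption, shown at 30%, 50% and 70%. The plan gives no accuracy figure to reproduce, and its sample size rests on mask filtration.

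**Step 1. What the MACE group reveals (the main point).** The only observable quantity is

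positive rate = prev × Se + (1 − prev) × (1 − Sp).

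This is one equation with three unknowns. Suppose the positive rate happens to equal the prevalence. Then

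Sp = 1 − prev × (1 − Se) / (1 − prev).

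For example, at prevalence 0.3 and Se 0.8: Sp = 1 − 0.3 × 0.2 / 0.7 = 0.914.

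| Prevalence | Se/Sp pairs giving the same positive rate |
|---|---|
| 30% | 100/100, 80/91, 30/70 |
| 50% | 100/100, 80/80, 50/50 |
| 70% | 100/100, 80/53, 70/30 |

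In the last pair of each row Se = 1 − Sp, so the result carries no information about varices. A perfect and a useless examination give the same data, and more patients would not separate them.

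**Step 2. What the EGD group adds.** It would supply the missing prevalence only if both groups had the same prevalence, and even then Se and Sp could not be separated. Without randomisation the prevalences may differ. As an example, take 30% in the EGD group and 60% in the MACE group, and a perfect EGD:

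- MACE that misses half of varices, with no false positives: 0.60 × 0.5 = 0.30 positive, identical to EGD.
- A perfect MACE: 0.60 against 0.30. Summing exactly over both binomials with 25 per group, Fisher's test is significant with probability 0.506.

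Here the poor examination looks equal to EGD, and the perfect one looks different about half the time.

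**Step 3. Illustration of a non-significant test.** Assume equal prevalence, perfect EGD and no MACE false positives, so that the EGD rate = prev and the MACE rate = prev × (1 − miss rate). The probability that Fisher's test is not significant is:

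| Share of varices missed by MACE | Prev 30% | Prev 50% | Prev 70% |
|---|---|---|---|
| 25% | 0.954 | 0.895 | 0.821 |
| 50% | 0.850 | 0.642 | 0.347 |
| 75% | 0.583 | 0.243 | 0.033 |

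The plan does not say that a non-significant result will be read as comparability. The table shows only that it could not be.

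**Step 4. If pairing is in fact intended.** With 25 pairs, the three prevalences give about 7, 12 or 17 patients with varices (25 × 0.3 = 7.5, 25 × 0.5 = 12.5 and 25 × 0.7 = 17.5, rounded down). If MACE detected all m of them, the exact (Clopper-Pearson) lower 95% limit for sensitivity is 0.025^(1/m): 59.0%, 73.5% or 80.5%. Agreement in 23 of 25 patients has an exact 95% interval of 74.0% to 99.0%.

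**The case against.** **This is an aerosol trial.** The title, primary endpoint and sample-size rationale all concern aerosol, and accuracy is not a listed endpoint. That is true, and the aerosol result is not compromised. But section IV names the diagnosis of varices in the trial's goal, and section V states the accuracy analysis under Methods. The absence of a matching endpoint is part of the contradiction and does not resolve it.

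**A paired design may be intended.** Section IX lists 50 capsule sets for 25 MACE patients, and section XI records the results of both examinations. If pairing is intended, the fault is incomplete description. This stands as an open question. Neither section says that a patient has both examinations: the extra sets could be spares, and the recording could be by group.

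**Effectiveness and utility are broad words.** They can cover completion and tolerability, which are measured. This stands in part. Those words need only be tied to the listed endpoints; accuracy and comparable performance clearly need a reference or a margin.

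**The scenarios are extreme.** Nothing in the documents supports miss rates of 50% to 75% or a twofold difference in prevalence, and sections V and X of the argument for MACE (the Abstract and the Background) cite favourable adult or Taiwanese experience. This is fair for Steps 2 and 3, which show what could happen and not what is likely. The conclusion rests on Step 1, which needs neither assumption.

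**Conclusion.** The concern holds, and the text must be corrected. As written, the trial cannot estimate the sensitivity or specificity of MACE, or its agreement with EGD, and it cannot support a statement of comparable diagnostic performance. This is a failure of identification, so neither a larger sample nor a later analysis would repair it. It holds at every prevalence examined.

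The conclusion depends on one reading: that no MACE patient also has EGD, which is what sections V, VIII and XII describe. The figures in Steps 1 to 4 rest on assumed prevalence, and those in Steps 2 and 3 also on assumed miss rates. The primary particle-count comparison and the listed secondary endpoints are outside this point.

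**What to change.** First reconcile section VIII with section IX (50 sets) and section XI (*both* examinations), and state whether any patient has both.

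**If none does:**
- Remove diagnostic accuracy as a planned analysis (section V) and the aim of comparable diagnostic performance (end of section VI).
- Limit effectiveness in diagnosis (section IV) and diagnostic utility (sections V and VI) to the listed endpoints.
- Add to section XII: *The proportion of patients in whom varices are reported will be given for each procedure with an exact 95% confidence interval, descriptively; it does not estimate accuracy. A p-value of 0.05 or more for varices detection will not be read as comparability.*

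**If pairing is already intended:**
- Say so, and for how many patients.
- Analyse those patients as pairs with EGD as the reference. Give exact confidence intervals for sensitivity and specificity and an interval for agreement. Do not apply the independent-group tests of section XII to paired results.
- State whether each reader knew the other result.
- Describe the findings by their intervals and not as comparable, since no margin is set.

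**Cost.** Changes to the aims and the analysis text, and one clarification. No extra procedure is requested. The price is a narrower diagnostic claim or, with existing pairs, the limited precision shown in Step 4.

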## **XII.Statistical Analysis and Sample Size Calculation**

We will analyze the results using STATA (version 17) and MedCalc (version 20) statistical software. Continuous variables will be analyzed using the Student t-test or Mann-Whitney U test to assess differences between the "study group" and the "control group." Categorical variables will be analyzed using the Chi-square or Fisher's exact test. A p-value of <0.05 will be considered the threshold for statistical significance. For the sample size calculation, we assume that the study group will wear surgical masks for the examination, which have an approximate filtration efficiency of 87-90%. Based on a 95% confidence interval and a 5% margin of error, we estimate that enrolling 50 subjects (25 in the study group and 25 in the control group) will provide sufficient power to detect statistically significant results.

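### The plan sets out to prove MACE efficient and safe, but offers only p<0.05 difference tests on 25 per group, with no confidence interval, margin or acceptable rate

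*Combined protocol and SAP*

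**What the plan says.** Section V (English Abstract), under scientific merits and anticipated results, states the intended conclusion: "we intend to prove the MACE is an efficient, safe and less aerosol-generating procedure than EGD".

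The outcomes that could bear on efficient and safe are secondary. Section VIII, under Droplet Particle Measurement, says: "The secondary endpoints are to analyze the examination completion rate, pain perception during the procedure, safety, and willingness to undergo the same examination again". The primary endpoint is the between-group difference in droplet particle count.

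Section XII is the whole analysis plan. For binary outcomes it says "Categorical variables will be analyzed using the Chi-square" or, as the alternative, Fisher's exact test. The decision rule is: "A p-value of <0.05 will be considered the threshold for statistical significance". It does not say which test applies when, whether the Chi-square is continuity-corrected, or whether the threshold is two-sided. It plans no confidence interval, and it sets no margin and no largest acceptable event or failure rate. The size is 25 per group.

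**The concern.** That MACE is safe is a claim that harm is absent or acceptably rare. That it is as completable as EGD is a claim of no important disadvantage. A test for a difference does not address either claim: a large p-value shows only that a difference was not detected. Since p<0.05 is the only criterion in the plan, a team that sees few events and p>=0.05 has nothing else in Section XII on which to rest the conclusion promised in Section V.

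At stake is a report that presents MACE as shown to be safe and efficient in biliary atresia patients older than 6 years, when the data would be compatible with a clearly worse adverse-event or completion rate. The risk is greater because Section XIII already starts from no reported adverse events with the device and Section XVIII lists no risks.

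**Working it through.** **Inputs.** From Section XII: 25 per group and a threshold of 0.05. Assumed: two-sided testing, because sidedness is not stated. The documents give no expected event or completion rate, so the splits and true rates below are illustrations.

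**The plan's own figure.** No size or power is given for completion or safety. The stated inputs (87-90% mask filtration, 95% confidence, 5% margin of error) give, by n = 1.96² p(1-p)/0.05², 174 at p = 0.87 and 139 at p = 0.90. The stated 50 is not reproduced. In any case these inputs concern particles, so the 50 was not derived from the safety or completion outcomes.

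**No events on MACE.** Exact (Clopper-Pearson) two-sided 95% upper limit for 0/25: 1 - 0.025^(1/25) = 0.137, or 13.7%.

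**k/25 on MACE against 0/25 on EGD.** With 25 per group the tests reduce to:

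- Fisher, two-sided: p = 2 × C(25,k)/C(50,k)
- Chi-square, uncorrected: X² = 50k/(50-k), 1 df
- Chi-square, Yates: X² = 50(k-1)²/[k(50-k)], 1 df

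| k | Expected events per group | Fisher p | Yates p | Uncorrected p |
|---|---|---|---|---|
| 3 | 1.5 | 4600/19600 = 0.235 | X² = 1.418, 0.234 | X² = 3.191, 0.074 |
| 4 | 2.0 | 25300/230300 = 0.110 | X² = 2.446, 0.118 | X² = 4.348, 0.037 |
| 5 | 2.5 | 106260/2118760 = 0.0502 | X² = 3.556, 0.059 | X² = 5.556, 0.018 |
| 6 | 3.0 | 354200/15890700 = 0.022 | 0.030 | 0.009 |

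Up to 3/25 against 0/25, every version is non-significant. At 4/25 and 5/25 the verdict depends on the version. From 6/25 all agree on significance.

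**What 3/25 against 0/25 leaves open.** If the three are failures to complete, completion is 88% against 100%. Wilson limits are 4.2% to 30.0% for 3/25 and 0% to 13.3% for 0/25. The Newcombe 95% interval for the difference is:

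- lower: 0.12 - √[(0.12-0.042)² + 0.133²] = -0.035
- upper: 0.12 + (0.300-0.12) = 0.300

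A result that is non-significant under every version is therefore compatible with an excess of up to 30 points on MACE.

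**Power at 25 per group, assumed true rates (MACE vs EGD).** When the EGD rate is 0, power is P(X>=6) for Fisher and P(X>=4) for the uncorrected Chi-square, with X binomial on 25. The third row comes from full enumeration.

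| True rates | Fisher | Uncorrected Chi-square |
|---|---|---|
| 15% vs 0% | 16% | 53% |
| 20% vs 0% | 38% | 77% |
| 20% vs 5% | 20% | 38% |

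**The case against.** The strongest reply is that nothing in the plan says p>=0.05 will be taken as proof of safety. Section VIII says only that the secondary endpoints will be analysed. The word prove sits in a passage on anticipated results, which is not a decision rule. Low power on secondary safety outcomes is also ordinary in a 50-patient study. This stands in part: the misreading is a risk and not a stated step. It does not remove the gap between the promised conclusion and the only method offered.

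Several stronger readings are tempting, and the documents do not support them:

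- **That 5/25 against 0/25 would count as non-significant, or that the tests almost never reject.** This holds for Fisher (0.0502, only just) and for Yates, but not for the uncorrected Chi-square, which Section XII equally allows (0.018). Power under that test is well above the Fisher values.
- **That the plan claims comparable safety or completion.** Section VI says "This study aims to evaluate whether MACE can achieve diagnostic performance comparable to traditional EGD", and that sentence concerns detection of varices only.
- **That the trial is declared powered for safety.** The phrase "will provide sufficient power to detect statistically significant results" names no endpoint, but it follows a mask-filtration assumption that can only concern particles.
- **That the whole quoted sentence is undermined.** Less aerosol-generating is a superiority claim on the primary endpoint, for which a difference test is the right type.

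One may add that expected counts this small normally lead to Fisher, so the disagreement between tests is partly academic. That is usual practice, but the plan does not state it.

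**Conclusion.** The point holds as a mismatch between conclusion and method on the secondary binary outcomes. Section XII contains nothing that could support the safe and efficient part of the Section V sentence, and 25 per group is too few for a null test result to do so. A clean record on MACE would still not exclude event rates up to 13.7%.

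This rests on two-sided testing, all 25 patients per group being evaluable, and completion being the nearest endpoint to efficient, a term the plan does not define. Pain, if analysed as a continuous score, falls outside these calculations. The matter should be corrected, but it does not threaten the primary comparison.

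**What to change.** In Section XII, for completion, adverse events and willingness to repeat:

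- report each group's proportion with an exact 95% confidence interval, and the risk difference with a 95% interval (for example Newcombe);
- name one test in advance for sparse tables: Fisher's exact where any expected count is below 5, which with equal groups of 25 means fewer than 10 events (or fewer than 10 non-events) in total;
- state that p>=0.05 will not be interpreted as evidence of safety or equivalence.

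In Section V, replace the intention to prove MACE efficient and safe with an intention to estimate its completion and adverse-event rates. Keep the aerosol comparison as the tested hypothesis.

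The cost is wording only, with no added patients or procedures. There are two consequences to accept. The safety statement becomes less favourable, for example: no events observed, rates up to 13.7% not excluded. Fisher also rejects less often than the uncorrected Chi-square and can differ from the interval at the edge: at 5/25 against 0/25 the Newcombe interval is 2.6 to 39.1 points while Fisher gives 0.0502. The plan should therefore say that the interval carries the interpretation.
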